5.4.4 Stage A2 evaluations during the study

Post registration

- M6620 (Berzosertib) schedule assignment
- Audiogram monitoring (if applicable)

Weekly Evaluations during treatment weeks 1 - 18

- Assessment of concomitant medications
- Weight
- ECOG performance status
- Physical examination
- Assessment of AE
- Assessment of DLT (Weeks 1-4 only)
- ECG (once per cycle, week 1 pre-treatment)
- Coagulation – INR, APTT or PTT (week one only, pre-cisplatin)

Additional evaluations during treatment weeks 1 - 18

- Venous blood sample within 72 hours prior to Cisplatin including:
 - Haematology – Hb, white blood cells (WBC) with differential count (neutrophils and lymphocytes) and platelets
 - Biochemistry – sodium, potassium, urea, creatinine, bilirubin, ALP and AST or ALT, Ca, Mg, Phosphate
- Venous blood samples within 24 hours prior to M6620 (Berzosertib) administration including:
 - Haematology – Hb, white blood cells (WBC) with differential count (neutrophils and lymphocytes) and platelets
 - Biochemistry – sodium, potassium, urea, creatinine, bilirubin, ALP and AST or ALT, Ca, Mg, Phosphate

Note: only one set of blood tests needs to be done if the timing satisfies both Cisplatin and M6620 (Berzosertib) requirements above.

- On days of M6620 (Berzosertib) monitor patient for reactions for 20 minutes after administration

Additional evaluation Week 4

- Audiogram monitoring (if applicable)

Additional evaluation Week 6, 12, 18

- CT chest abdomen and pelvis to assess response

Evaluations at 2 & 8 week follow up

- Venous blood samples:
 - Haematology – Hb, white blood cells (WBC) with differential count (neutrophils and lymphocytes) and platelets
 - Biochemistry – sodium, potassium, urea, creatinine, bilirubin, ALP and AST or ALT, Ca, Mg, Phosphate
- Assessment of concomitant medications
- Weight, ECOG performance status
- Physical examination
- Coagulation – INR, APTT or PTT (week 2 only)
- Assessment of AE
- CT chest abdomen and pelvis to assess response (week 26 only)

5.4.5 Stage A2 evaluations on early withdrawal

Where possible, patients will be followed up as per the follow up visits at 2 and 8 weeks post end of treatment, including assessments of AEs and DLTs (see section 6).

5.4.6 Stage A2 off-Study and Follow-up Evaluations

The final study visit will occur 8 weeks after completion of treatment. Patients should be counselled on the continued use of contraception for 6 months following the end of treatment **if appropriate** and encouraged to report any pregnancies to the study team. The clinician in charge will be asked to provide the following reports at 6 & 12 months.

- date and cause of death, if applicable
- date and site of progression
- details of any clinically significant events
- further chemotherapy or other intervention required

5.5 Stage B evaluations

Post registration and prior to start of Induction chemotherapy

- Research blood sample
- Audiogram monitoring (if applicable)

5.5.1 Stage B evaluations during the study

Evaluations during treatment weeks 1 & 4 (induction chemotherapy + M6620 (Berzosertib)) and weeks 7, 8, 9, 10 & 11 (chemoradiotherapy + M6620 (Berzosertib))

- The following assessments should be done within 24 hours prior to M6620 (Berzosertib) administration: Venous blood samples within 24 hours prior to M6620 (Berzosertib) administration including:
 - Haematology – Hb, white blood cells (WBC) with differential count (neutrophils and lymphocytes) and platelets
 - Biochemistry – sodium, potassium, urea, creatinine, bilirubin, ALP and AST or ALT, Ca, Mg, Phosphate
- Assessment of concomitant medications
- Weight
- ECOG performance status
- Vital signs: systolic/diastolic blood pressure (BP), pulse rate, temperature
- Physical examination
- ECG (weeks 1, 4, 7 and 10 pre-cisplatin treatment)
- Coagulation (INR, APTT or PTT, week 1 only pre-cisplatin)
- Mellow score
- Assessment of AE
- Assessment of DLT (not week 1)

The following assessments should be done on days of M6620 (Berzosertib) administration during induction chemotherapy. If problems were identified, this should be continued during chemoradiotherapy:

- Monitor patient for reactions for 20 minutes after administration of M6620 (Berzosertib)

Additional assessments weeks 1, 4, 7 & 10

- Venous blood sample within 72 hours prior to Cisplatin including:
 - Haematology – Hb, white blood cells (WBC) with differential count (neutrophils and lymphocytes) and platelets
 - Biochemistry – sodium, potassium, urea, creatinine, bilirubin, ALP and AST or ALT, Ca, Mg, Phosphate

Note: only one set of blood tests needs to be done if the timing satisfies both Cisplatin and M6620 (Berzosertib) requirements above.

Additional evaluation week 4

- Audiogram monitoring (if applicable)

Additional assessments week 7 (see section 7.3 for details)

- Research endoscopy and biopsy
- Research blood sample

Radiotherapy planning should take place in weeks 2 to 4 and M6620 (Berzosertib) schedule assignment will take place in week 6

Evaluations during induction chemotherapy weeks 2 & 5

Evaluations to be done on day 1 or day 2:

- Assessment of concomitant medications
- ECOG performance status
- Vital signs: systolic/diastolic blood pressure (BP), pulse rate, temperature
- Physical examination
- Mellow score
- Assessment of AE
- Assessment of DLT

Evaluations at weeks 12 & 18

- Venous blood samples:
 - Haematology – Hb, white blood cells (WBC) with differential count (neutrophils and lymphocytes) and platelets
 - Biochemistry – sodium, potassium, urea, creatinine, bilirubin, ALP and AST or ALT, Ca, Mg, Phosphate
- Assessment of concomitant medications
- ECOG performance status
- Vital signs: systolic/diastolic blood pressure (BP), pulse rate, temperature
- Coagulation (INR, APTT or PTT, week 12 only)
- Physical examination
- Mellow score
- Assessment of AE
- Assessment of DLT
- Research blood sample (week 12 only)

Evaluations at week 24

- Assessment of concomitant medications
- ECOG performance status
- Vital signs: systolic/diastolic blood pressure (BP), pulse rate, temperature
- Physical examinations
- ECG
- Mellow score
- Assessment of AE
- Assessment of DLT
- Endoscopy and research biopsy
- CT chest abdomen and pelvis to assess response

5.5.2 Stage B evaluations on early withdrawal

Where possible, patients will be followed up as per the follow up visits which should be brought forward to 1, 7 and 13 weeks post end of treatment, including assessments of AEs and DLTs see section 6.

5.5.3 Stage B off-Study and Follow-up Evaluations

The final study visit will occur 13 weeks after completion of treatment. Patients should be counselled on the continued use of contraception for 6 months following the end of treatment **if appropriate** and encouraged to

report any pregnancies to the study team. Sites will report this if notified up until 6m or 13w after last patient treatment whichever is sooner.

6 EARLY PATIENT WITHDRAWAL

The Trial Office should be informed of any early patient withdrawal within 24 hours of the site becoming aware using the Early Withdrawal Form and scan and email as a PDF attachment to [contact]. If the reason for early withdrawal is an SAE then an SAE Form will also be required.

6.1 Treatment Withdrawal

During the course of the trial, a patient may withdraw early from treatment. This may happen for a number of reasons, including:

- Unacceptable toxicity
- AE/SAEs requiring discontinuation
- Loss to follow-up
- Significant protocol deviation or inability to comply with trial procedures
- Clinical decision
- Patient decision

When the patient stops treatment early, the 'End of Treatment' Form needs to be completed, and any other relevant CRFs (example SAE Form). Any evaluations carried out on early withdrawal will be captured as per sections 5.4.2, 5.4.5 and 5.5.2. The reason for withdrawing from treatment early should be clearly documented in the medical records.

The end of treatment means the patient will then enter the routine follow up stage of the trial. If M6620 (Berzosertib) treatment is stopped, the patient will continue with standard treatment and will be followed up as part of the trial.

6.2 Consent Withdrawal

Consent withdrawal means that a patient has expressed a wish to withdraw from the study altogether. Under these circumstances, the site needs to document all relevant discussions in the patient notes and notify the Trial Office, which will allow the office to mark all future CRFs as not applicable. The site should inform the Trial Office whether any samples already collected for the study should be destroyed.

Under these conditions, investigators are still responsible to follow up any SAEs till resolution.

6.3 Patient evaluability and replacement

Patients will not be replaced since TiTE-CRM uses accumulated data and all patients will be evaluable for dose escalation decisions. However, the TMG may decide to replace patients if drop-out occurs early in the treatment schedule for reasons other than a DLT.

In Stage B, all patients who receive treatment within the study will be evaluable for response. All participants who receive one dose of M6620 (Berzosertib) will be evaluable for the safety analysis.

Evaluable for Objective Response. Only those patients who have measurable disease present at baseline, have received at least one cycle of therapy, and have had their disease re-evaluated will be considered evaluable for response. These patients will have their response classified according to the definitions stated in Appendix B. (Patients who exhibit objective disease progression prior to the end of cycle 1 will be considered evaluable.)

Evaluable Non-Target Disease Response. Patients who have lesions present at baseline that are evaluable but do not meet the definitions of measurable disease, have received at least one cycle of therapy, and have had their disease re-evaluated will be considered evaluable for non-target disease. The response assessment is based on the presence, absence, or unequivocal progression of the lesions.

7 SAMPLES FOR LABORATORY ANALYSIS

7.1 Samples to be analysed in local Trust's laboratories

Diagnostic Laboratories

Samples for haematology and biochemistry analysis will be labelled with standard patient identifiers and sent to the local hospital diagnostic laboratory. Results will be processed in the standard way and entered into the routine hospital reporting system. Samples will be stored, held, reported and subsequently destroyed in accordance with standard local laboratory practice.

Pathology

The routine diagnostic pathology samples and additional research samples taken at endoscopy will also be labelled, processed and reported according to the standards proposed by the Royal College of Pathologists. An anonymised copy of the diagnostic histopathology/cytology report should be sent to the Trial Office at registration.

7.2 Blood and Tissue samples for translational research

Blood and biopsy samples will be collected in Stage B for translational research concerning the mechanism of action of M6620 (Berzosertib).

7.2.1 Biopsy samples

Tissue samples will be collected at least 24 hours after the first dose of M6620 (Berzosertib) treatment. The samples will be analysed for a signal of ATR inhibition by M6620 (Berzosertib) following induction of the DDR (ATR activity) by Cisplatin or RT treatment.

Tissue should be biopsied from 3 areas of the oesophagus: normal tissue outside the radiotherapy field, normal tissue within the radiotherapy field and tumour tissue within the radiotherapy field. This will allow a comparison of the effect of M6620 (Berzosertib) on healthy tissue, irradiated tissue and tumour tissue.

All participants will have a diagnostic biopsy prior to screening. Baseline FFPE tissue samples will be analysed for common genetic mutations using a cancer panel.

Timepoints for endoscopy and biopsy:

- week 7 day 3, and if M6620 (Berzosertib) given carried out at least 24 hours after the administration of M6620 (Berzosertib) (on treatment biopsy should be taken from fraction 3 to fraction 5 (but up to fraction 7 is permitted if required)
- week 24

Samples will be sent to the central lab for IHC analysis (see Sample Handling Manual for further details).

Remaining samples will be returned to Oxford for further IHC markers and storage in Oxford research biobank (details will be in the sampling handling manual).

7.2.2 Research blood samples

Blood samples will be collected to look for biomarkers for ATR inhibition and to identify other DNA, RNA or protein markers present in oesophageal cancer.

Timepoints for research blood samples:

- prior to starting treatment
- week 7 from fraction 3 to fraction 5 (but up to fraction 7 is permitted if required)
- week 12

Samples will be sent to Oxford University Labs for analysis (details will be in the sampling handling manual).

7.3 Labelling and confidentiality of samples sent

All samples sent to analytical Laboratories will be labelled with the trial code, trial patient number, schedule and date/time taken. Should a laboratory receive any samples carrying unique patient identifiers the recipient must immediately obliterate this information and re-label.

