3.2 Stage B

Primary Objective	Endpoints/ Outcome measures	Time point(s) for evaluation of end point
• To determine the best tolerated M6620 (Berzosertib) treatment schedule (or phase II recommended dose (RPTD)) administered concomitantly with radiotherapy (dCRT) in combination with cisplatin and capecitabine in the radical treatment of oesophageal cancer	Highest treatment schedule resulting in less than 45% dose limiting toxicity (DLT) rate (see section 9.1.2 for DLT definitions)	
 • Up to Week 24
Secondary Objectives	Endpoints/ Outcome Measures	
• To determine the safety and toxicity profile of M6620 (Berzosertib) administered concomitantly with dCRT in combination with cisplatin and capecitabine in the radical treatment of oesophageal cancer	
 • Any toxicity grade ≥ 3 graded according to CTCAE v4.03 and length of time for toxicity to resolve 	
 • Up to week 24
• To determine tolerance and ability to deliver M6620 (Berzosertib) in combination with standard dCRT	
 • Treatment tolerance and deliverability measured by proportion of patients completing at least 80% of the planned chemotherapy dose and at least 20 fractions of RT 	
 • End of induction chemotherapy and dCRT. End of week 11
• Efficacy and safety of the combination	
 • Objective tumour response (OR) as evaluated by CT scan and quantified by Response Criteria Evaluation (RECIST 1.1) and endoscopic and biopsy findings. • PFS and OS from D1 	
 • 24 weeks
Tertiary/Exploratory Objectives	Endpoints/ Outcome Measures	

 • To explore target effects in tissue 	
 • Change in level of ATR inhibition and apoptosis in M6620 (Berzosertib) treated tissue using IHC. • Genotyping of tumours • Aim to identify markers for oesophageal cancer in the blood 	
 • Biopsies at baseline, week 7 and 24 • Blood samples at baseline, week 7 and week 12
---	--	--

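### Section 7.3 puts the M6620 schedule and sampling time on every laboratory sample, and neither document provides for masked scoring of the Stage B immunohistochemistry endpoint

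*Protocol*

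**What the plan says.** Protocol section 7.3 sets the labelling rule for all samples leaving the sites: "All samples sent to analytical Laboratories will be labelled with the trial code, trial patient number, schedule and date/time taken". Schedule is the Protocol's term for the M6620 allocation (Tables 8.1 to 8.3). The same section tells a laboratory to obliterate unique patient identifiers and re-label if it receives any. That step protects confidentiality and leaves the schedule in place.

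The endpoint most exposed is the first Stage B tertiary/exploratory measure in section 3.2: "Change in level of ATR inhibition and apoptosis in M6620 (Berzosertib) treated tissue using IHC", with time points given as "Biopsies at baseline, week 7 and 24". Section 7.2.1 adds a comparison by site. It says "Tissue should be biopsied from 3 areas of the oesophagus" and, of the three sites, "This will allow a comparison of the effect of M6620 (Berzosertib) on healthy tissue, irradiated tissue and tumour tissue". It sends the biopsies to a central laboratory for IHC and refers to the Sample Handling Manual for detail. Tissue site is not among the label fields listed in 7.3.

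On masking, Protocol section 2 describes a single-arm, open-label trial. SAP section 3.9 rules out blinded analysis on the ground that the trial is not randomised. SAP section 7.2.3 leaves tertiary outcomes out of the SAP. None of these refers to the people who score the assays.

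**The concern.** IHC scoring can involve judgement. The endpoint is a change in treated tissue, so a scorer who knows which sample came before treatment and which came on treatment may expect a particular direction. The label supplies that knowledge: patient number groups the samples, and date/time orders them. It also discloses the assigned schedule, for which section 7.3 states no laboratory use.

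What is at stake is the credibility of the only listed endpoint that measures target effect in tissue. Patients undergo a research endoscopy and biopsy in week 7 for it (section 5.5.1). Stage B has at most 25 patients, with a minimum of 15 expected. The SAP prespecifies no analysis of this endpoint, so it offers no later safeguard.

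**Working it through.** The plan states no figure to reproduce. The check sets the sections side by side and counts doses.

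**1. What each label field discloses, and whether the plan needs it.**
- *Patient number with date/time*: together these can show the order of baseline, week 7 and week 24 samples, which is the contrast that a change endpoint rests on. Date/time also has a legitimate use. Section 7.2.1 requires the week-7 biopsy to follow M6620 by 24 hours or more, and says "on treatment biopsy should be taken from fraction 3 to fraction 5", with up to fraction 7 allowed. Compliance cannot be checked without a sampling time, but the person scoring the slide does not need it.
- *Schedule*: no use at the laboratory is stated.

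**2. What schedule reveals about exposure.** All Stage B schedules share two induction doses (Protocol Table 8.3). Radiotherapy starts on a Monday and runs on weekdays, so fractions 3 to 5 fall on chemoradiotherapy days 3 to 5, and fractions 6 and 7 on days 8 and 9. Because of the 24-hour rule, a biopsy on day 5 or day 9 must precede any dose due that day. Chemoradiotherapy doses scheduled before the biopsy are:

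| Biopsy | Source | Schedule -1 | Schedule 1 | Schedule 2 |
|---|---|---|---|---|
| Fractions 3-5 | Protocol Table 8.3 | 1 | 1 | 1 |
| Fractions 3-5 | SAP Table 4 | 0 | 1 | 1 |
| Fractions 6-7 | Protocol Table 8.3 | 1 | 2 | 2 |
| Fractions 6-7 | SAP Table 4 | 0 | 2 | 2 |
| Week 24 | Protocol Table 8.3 | 5 | 7 | 10 |
| Week 24 | SAP Table 4 | 4 | 7 | 10 |

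By the Protocol table, a biopsy in the main window follows the same M6620 exposure on every schedule. Any schedule gradient at that point could not reflect doses received, yet the label tells the scorer which schedule was assigned. The two tables disagree on whether schedule -1 has a day-2 dose. That is a separate matter, and the tables must be reconciled.

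**3. Is masking provided anywhere?** Sections 7.2.1, 7.2.2, 7.3 and 7.4 of the Protocol and sections 3.5, 3.9, 6.4 and 7.2.3 of the SAP contain no provision for coded or masked assay scoring. The Sample Handling Manual is the one place named that could contain it.

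**4. Can a bias be sized?** That would need a scoring method, a between-reading variance, a plausible scorer shift and a planned comparison. The documents give none of these. No between-schedule IHC test is specified, and numbers per schedule will follow from adaptive allocation. Schedule -1 is opened only if schedule 1 proves too toxic. Any figure would rest on assumed inputs, so none is offered.

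**The case against.** The strongest reply is that section 7.3 governs the label on samples in transit and does not govern what is visible on a slide at scoring. The central laboratory may re-code on receipt, and the Sample Handling Manual may require it. This stands. A reader might infer from 7.3 that IHC is scored unmasked, but the documents do not support that. They show only that the identifying information is sent and that no masking is provided for in the text available.

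Second, the label fields are not all gratuitous. A reader might conclude that they serve no purpose. That is wrong for date/time, which is needed to check the sampling windows. For schedule, it can be said only that no purpose is stated.

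Third, the stakes are low. The endpoint is exploratory, section 7.4 says assay results are not meant to influence care, and nothing here feeds the dose-limiting toxicity endpoint, schedule allocation or the stopping rules. This also stands, and it limits the severity.

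Fourth, the trial is open-label and SAP 3.9 rules out blinded analysis. This does not answer the point. Open treatment does not require open assay scoring, and laboratory scorers can be masked in a single-arm trial.

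Finally, masking may be imperfect. Baseline tissue is the diagnostic biopsy taken before screening, while the research sets come from three sites, and radiation change may be visible. This weakens masking of time point but gives no reason to leave the schedule on the label.

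**Conclusion.** The point holds in a limited form. The Protocol requires schedule and sampling time on every sample sent to the laboratories, and neither document provides for IHC scoring to be masked to them. The exposure lies mainly in the within-patient baseline, week 7 and week 24 contrast. A reader might fear a scorer-made dose-response across schedules. The documents support that less well, because the Protocol table gives equal prior exposure in the main week-7 window and no between-schedule IHC comparison is planned.

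No size of bias can be derived. Severity is low, and the change is a cheap improvement to an exploratory endpoint. The conclusion assumes that scoring involves some judgement, which the documents do not describe, and that the Sample Handling Manual does not already require coding. If it does, a cross-reference and a shorter label would settle the matter.

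**What to change.** In section 7.3, delete schedule from the label. Keep collection date/time on the transport log and with the Trial Office, so that the 24-hour and fraction windows can still be checked. Add one sentence, repeated in the Sample Handling Manual, requiring that slides or aliquots be coded with a non-informative ID before scoring. Tissue site should be kept where the assay needs it, and scores should be linked to schedule and time point only after they are locked. If the manual already requires this, say so in 7.3.

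The cost is a revised label template, a linking list held by the Trial Office, and some coding work. It needs no extra sample, visit or scorer. Reading each patient's samples together in one batch is optional, since it would hold week-7 material until week 24. The timing is convenient: SAP section 1.2 says the plan will be updated for Stage B before that stage opens to recruitment.

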7.4 Clinical reporting of exploratory research assay results

The results of the CHARIOT trial research assays are exploratory and are not intended to influence the individual patient's medical care. Findings will not be reported routinely to the responsible clinician except in the unlikely event that the result might be beneficial to the patient's clinical management.

7.5 Trial sample retention at end of study

The Chief Investigator has overall responsibility for custodianship of the trial samples. Laboratories are instructed to retain any surplus samples pending instruction from the Chief Investigator on use, storage or destruction. It is possible that new or alternative assays may be of future scientific interest. At the end of the research study any surplus samples may be retained for use in other projects that have received ethical approval. Hence, any surplus study samples may be transferred to a licensed tissue bank where they will be managed in accordance with applicable host institution policies and the Human Tissue Act (HTA) requirements.

